6.0 DOSE MODIFICATIONS

6.1 Radiation therapy Dose Modications

Radiation therapy modification is at the discretion of the treating physician as per routine clinical care.

Concomitant temozolomide, if radiotherapy is interrupted

If radiotherapy has to be temporarily interrupted for technical or medical reasons unrelated to the temozolomide administration, then treatment with daily temozolomide should continue. If radiotherapy has to be permanently interrupted then treatment with daily temozolomide should stop. Temozolomide can resume with the initiation of the adjuvant phase of treatment.

6.2 Temozolomide Dose Modifications

Temozolomide dosage modification is at the discretion of treating physician as per routine clinical care.

On day 1 of each cycle (+/- 7 days), ANC $\geq 1.5 \times 10^9/L$, platelet count $\geq 100 \times 10^9/L$ and all treatment-related grade 3 or 4 non-hematologic AEs (except nausea and vomiting unless the patient has failed maximal antiemetic therapy and fatigue) must have resolved (to grade ≤ 1).

6.3 Disulfiram Dose Modifications

If a patient experiences any grade 2 or higher non-hematologic toxicity considered by the investigator to be possibly, probably, or definitely related to DSF, the dose of DSF may be decreased by 50% (i.e., from 125 mg BID to 125 mg qd – and when taken with temozolomide to be administered within 6-8 hours prior to temozolomide dose) once. Special attention should be paid to neurological symptoms such as delirium/psychosis, gait disturbance/ataxia, and peripheral neuropathy. A grade 2 toxicity of the above neurological symptoms should prompt a consideration for further work-up and dose reduction.

No second dose reduction is allowed—if a second dose reduction is required, DSF and Cu will be discontinued and the patient will be taken off study. Of note, hematologic toxicity is uncommon for DSF and is likely related to temozolomide.

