4.4.3 Central Nervous System Effects

Doses of 500-1000 mg of DSF per day with adjuvant temozolomide produced neurological toxicities in some patients, including delirium/psychosis, ataxia, and peripheral neuropathy, especially at the 1000 mg dose. Patients should be carefully monitored for early signs of these symptoms. Once other causes such as tumor progression are ruled out, dose reduction of DSF to 125 mg (half of 250 mg tablet) once a day should be considered if the toxicity is grade 2 or greater (refer to Section 6.2). If symptoms are not improving with dose reduction, DSF should be discontinued. Patients whose symptoms are not considered immediately life-threatening should be carefully monitored. Each patient may be approached individually with a systematic assessment to rule out other causes. Appropriate tests may include vital signs measurement, computerized tomography, MRI scans, or other appropriate medical assessment.

If the patient's level of consciousness is considered to be life-threatening, the patient should be hospitalized and necessary measures should be instituted to secure the airway, ventilation, and intravenous access.

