4.5 Duration of Therapy

Patients demonstrating continued benefit from the adjuvant temozolomide after 6 cycles can continue treatment to a maximum of 12 cycles.

If at any time the constraints of this protocol are considered to be detrimental to the patient's health and/or the patient no longer wishes to continue protocol therapy, the protocol therapy should be discontinued and the reason(s) for discontinuation will be documented.

In the absence of treatment delays due to adverse events, DSF-Cu treatment may continue until:

- Documented and confirmed disease progression
- Death
- Adverse event(s) that, in the judgment of the investigator, may cause severe or permanent harm or which rule out continuation of study drug
- Patient develops unacceptable toxicity deemed possibly, probably, or definitely related to drug that does not resolved to grade 1 or to the patient's baseline status
- Patient requires more than 1 dose reductions
- General or specific changes in the patient's condition render the patient unacceptable for further treatment in the judgment of the investigator
- Serious noncompliance with the study protocol
- Lost to follow-up
- Patient withdraws consent
- Investigator removes the patient from study
- The investigator, or the investigator's institution decides to close the study

In the case of tumor progression, both temozolomide and DSF-Cu should be discontinued, and patient should be considered for second-line therapy. If temozolomide is temporarily withheld due to toxicity, DSF-Cu should be continued until temozolomide may be resumed again. If temozolomide is discontinued, DSF-Cu may be continued as per the discretion of the treating physician. If DSF-Cu is discontinued due to toxicity, temozolomide may be continued as per the discretion of the treating physician.

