8.1.3 Supplier

ANII Clinical Research Team together with the Aurora Saint Luke's Pharmacy Committee will decide upon a US unique manufacturer / supplier of DSF. Aurora Pharmacy Committee will ensure that for the purposes of the study that Aurora Saint Luke's dispensing pharmacy will ensure cutting DSF 250 mg tabs into halves.

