8.1.4 Dosage Form

DSF will be supplied in roughly 125 mg per dose (one half of 250 mg tab).

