APPENDIX C: Disulfiram and Copper Medication Diary

Today's Date: _____ Agent: Disulfiram/Copper Month: _____

Patient Name: _____

INSTRUCTIONS TO THE PATIENT:

1. Complete one form for each month. Take ___ mg (___capsule) of disulfiram two times a day with meals with breakfast and dinner). Please also take 2 mg of copper gluconate supplement two times a day with each meal. Do **not** take disulfiram or copper within one hour of your dose of temozolomide.
2. Record the date, and how many times you took disulfiram and copper on that date.
3. If you have any questions or notice any side effects, please record them in the comments section. Record the time if you should vomit.
4. Please return the forms to your physician or your study coordinator when you go to your next appointment. Please bring your unused study medications and/or empty bottles with you to each clinic visit so that a pill count can be done.
5. Avoid consuming alcohol before and throughout the entire study.

Day	Date	Check each time you take your disulfiram dose			Check each time you take your copper dose			Comments
		Breakfast	Lunch	Dinner	Breakfast	Lunch	Dinner	
1								
2								
3								
4								
5								
6								
7								
8								
9								
10								
11								
12								
13								
14								
15								
16								
17								
18								
19								
20								
21								
22								
23								
24								
25								
26								
27								
28								

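### The only disulfiram/copper diary prints a twice-daily schedule, so it misstates the once-daily reduced dose unless staff correct it by hand

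*Combined protocol and SAP*

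**What the plan says.** Section 4.2 sets the full DSF dose at 125 mg twice daily with meals, 250 mg/day in total, with 2 mg of copper gluconate alongside each DSF dose.

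Section 6.3 covers grade 2 or higher non-hematologic toxicity that is at least possibly related to DSF. In that case "the dose of DSF may be decreased by 50% (i.e., from 125 mg BID to 125 mg qd", once only. When the reduced dose is taken with temozolomide, 6.3 places it 6 to 8 hours ahead of the temozolomide dose. Section 4.4.3 names the same level for neurological toxicity: "dose reduction of DSF to 125 mg (half of 250 mg tablet) once a day should be considered".

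Appendix C is the only DSF/copper diary; Appendices D and E are for temozolomide. It has blanks for mg and capsule count, followed by fixed text: "of disulfiram two times a day with meals with breakfast and dinner". Copper is also fixed, at 2 mg twice a day.

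On supply, Section 8.1.3 says the "dispensing pharmacy will ensure cutting DSF 250 mg tabs into halves", and Section 8.1.4 says "DSF will be supplied in roughly 125 mg per dose (one half of 250 mg tab".

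Three passages say what follows if a reduction does not work. Section 4.4.3: "If symptoms are not improving with dose reduction, DSF should be discontinued". Section 6.3: "if a second dose reduction is required, DSF and Cu will be discontinued and the patient will be taken off study". Section 4.5 lists as a stopping reason: "Patient requires more than 1 dose reductions".

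**The concern.** The dose rule changes the one item the form fixes, and leaves unchanged the one item the form lets staff fill in. The entry is 125 mg at both dose levels, so an unedited diary reads the same for a patient on full dose and a patient on reduced dose. No section tells staff to amend or replace the page after a reduction. Each page covers a month, so a patient reduced mid-month already holds a page with the twice-daily instruction.

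The patients affected are those who already have DSF-related toxicity, and 6.3 singles out delirium or psychosis, ataxia and neuropathy. A patient who follows the printed page stays at full dose while the clinician believes the dose has been halved. If symptoms persist, the clinician may conclude that a reduction failed when it was never taken. The patient could then lose DSF under 4.4.3, or lose DSF and copper and leave the study under 6.3.

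**Working it through.** The arithmetic is daily dose = mg per administration x administrations per day. No sample-size, power or error-rate calculation is involved.

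1. **Full dose (4.2).** 125 mg x 2 = 250 mg/day, which reproduces the protocol's stated total.
2. **Reduced dose (6.3, 4.4.3).** 125 mg x 1 = 125 mg/day. 125 / 250 = 50%, which reproduces the stated 50% decrease.
3. **Diary as printed, with 125 mg entered (Appendix C).** 125 mg x 2 = 250 mg/day. The reduction is (250 - 250) / 250 = 0%, and the difference from the intended level is 250 - 125 = 125 mg/day, one half-tablet.
4. **Could another entry rescue the printed frequency?** It would have to be 125 / 2 = 62.5 mg per dose. That is not the level in 6.3, and the smallest unit supplied under 8.1.3 and 8.1.4 is 250 / 2 = 125 mg. So the form has to be edited by hand or replaced.
5. **Copper.** Under 4.2, one DSF dose a day carries 2 mg x 1 = 2 mg/day. Appendix C prints 2 mg x 2 = 4 mg/day. Section 6.3 gives no copper dose at the reduced level. Section 8.1.11 points both ways: it states twice daily, and it also says copper is taken at the same time as DSF. Once daily therefore follows from 4.2, not from 8.1.11.
6. **Timing.** Section 4.2 puts adjuvant temozolomide at bedtime. A dose 6 to 8 hours before that does not clearly coincide with breakfast or dinner, the two meals printed on the diary. Appendix C mentions only the one-hour separation from temozolomide. On temozolomide days the page therefore lacks the timing of the reduced regimen as well as its frequency.

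**The case against.** The case for leaving this alone is substantial.

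- **The dose rule is consistent.** Sections 6.3 and 4.4.3 agree. Appendix C is a patient record that staff complete each month, and its grid already has a lunch column that a twice-daily drug does not need. A once-daily dose can be recorded on it. This stands, and it makes the problem one of form wording. It does not remove the printed instruction above the grid.
- **Harm needs several failures in a row.** Staff must leave the frequency uncorrected, the patient must follow the page over the clinician's instruction, and the checks must miss it. The diary records how often each drug was taken, pill counts are made at visits, and visits are about every 4 weeks, with more contact during radiation. Section 4.4.3 also asks for careful monitoring. This stands, although the diary and pill count detect an error only after doses have been taken.
- **Staying at 250 mg/day is not an overdose.** It is the protocol dose, half the 500 mg/day maximum tolerated dose cited in 1.7, and within the 250-500 mg/day range cited in 1.9. The reduction is also permissive: 6.3 allows it and 4.4.3 asks that it be considered. A reader might infer that the diary exposes patients to a dose the protocol forbids; it does not. What remains is that a clinician who chose to reduce intends 125 mg/day, and the page says otherwise.
- **Cumulative excess.** A reader might multiply 125 mg/day over a cycle, for example 28 x 125 = 3,500 mg. That assumes 56 half-tablets are dispensed per 28 days and nothing is noticed. If supply were matched to once daily at 28 half-tablets, it would run out on day 28 / 2 = 14, after 14 x 125 = 1,750 mg. If staff correct the form, the excess is 0. The documents state no dispensing quantity, so no single total is supported.

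**Conclusion.** The mismatch holds as a minor patient-safety correction. If 125 mg is entered and the page is not corrected by hand, Appendix C instructs 250 mg/day where 6.3 intends 125 mg/day: 0% reduction instead of 50%. The wording is certain; the consequence is conditional on the form being left as printed and followed. The documents do not say how often the reduced level will be used, so expected frequency cannot be estimated.

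Two stronger readings should be resisted. A reader might infer that the error would bias the efficacy results through patients wrongly taken off study. The documents give no rate of reduction or of form error to support that, and no endpoint definition, sample size or error rate changes. A reader might also infer that the protocol already settles reduced-level copper at 2 mg once daily. That follows from 4.2, but 8.1.11 also says twice daily, so it needs to be stated.

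**What to change.** In Appendix C, make the DSF and copper frequency, and the meal or clock time of dosing, fill-in fields. Alternatively, issue a separate once-daily reduced-dose page. Either version should carry 6.3's instruction to take the reduced dose 6 to 8 hours before temozolomide on temozolomide days. A frequency blank alone would leave breakfast and dinner printed.

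In 6.3, state that copper at the reduced level is 2 mg once daily with the DSF dose, in line with 4.2, and add an exception for reduced patients to 8.1.11.

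Three clerical edits can go in the same amendment: the same exception in 8.1.6 and in study calendar footnote 4, and the cross-reference in 4.4.3, which sends the reader to 6.2 (temozolomide) when 6.3 is meant.

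The cost is one reprinted diary page and a few lines of amendment text. No visits, procedures or patients are added.

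Until the amendment is in place, staff who reduce a dose should strike out the printed frequency, write in the once-daily schedule and replace any page the patient already holds.

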6.3.1 Administration of DSF to Patients with Abnormal Hepatic Function

DSF-Cu should only be administered if hepatic function is within the parameters established in the eligibility criteria. Hepatic toxicity from DSF-Cu is uncommon but may occur. Therefore, hepatic dysfunction that occurs while the patient is on study should prompt an evaluation to determine the cause, including the possibility of hepatotoxicity from concurrent medications.

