1.9 Toxicology and Safety

DSF has been used clinically to treat alcoholism for more than 60 years, so its safety profile is well known. Early toxicology studies done in mice, rats, dogs, and rabbits have shown that DSF has very low toxicity, with LD_{50} between 1.8-10g/kg when administered orally.

At those extreme doses, demyelination of brain and spinal cord was observed on histopathology (Child and Crump 1952). Interestingly, long-term administration of high doses of DSF to rats did not induce any laboratory or histological signs of liver damage (Milandri, et al. 1980). High doses of DSF (up to 6 g daily) are relatively nontoxic in humans. Symptoms of overdose include vomiting, headache, apathy, ataxia, motor restlessness, irritability, hallucinations, psychosis, loss of consciousness and convulsions. Death occurs by respiratory arrest, preceded by ascending paralysis, and pathological lesions are seen in the liver, spleen, kidney and CNS, with congestion in the adrenal gland and edema in the heart muscle.

The current FDA-recommended dose of DSF is 250-500 mg daily for alcohol abstinence. In early clinical practice, a much higher dose of 1000-3000 mg per day was used (Fuller and Gordis 2004). At high dosages, the DSF-ethanol reaction may be severe and even fatal, but such high dosage in the absence of alcohol is well tolerated. In the early 1950s, 4 patients (out of an estimated 11,000 patients prescribed high doses of DSF) died of sudden respiratory or cardiovascular causes likely related to the DSF-ethanol reaction (Jacobsen 1952). At such high dosages, there were also case reports of psychosis in the absence of alcohol ingestion (Guild and Epstein 1951; Martensen-Larsen 1951). A phase I study administered a single dose of oral DSF prior to cisplatin every 3 weeks and encountered dose-limiting reversible confusion at 3000 mg/m² (approximately 4800 mg) (Stewart, et al. 1987). High doses of DSF may inhibit cerebrospinal dopamine B-hydroxylase (Nilsson, et al. 1987), and people with very low activity of dopamine hydroxylase may be prone to transient psychosis with such inhibition (Major, et al. 1979). In another phase I study of non-metastatic recurrent prostate cancer patients treated with 250-500 mg of DSF alone, grade 3 toxicities included double vision, hearing loss, LFT abnormality, diarrhea, constipation, and ataxia (Schweizer, et al. 2013).

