1.11 Study Rationale

Patients with unmethylated glioblastoma respond poorly to current standard treatment and have a poor prognosis.

Although standard post resection radiation therapy may provide a survival benefit of approximately two months, delayed radiation at or after 8 weeks has been shown to not increase overall survival. This study proposes standard of care treatment with 6 – 6 1/2 weeks of radiation with concurrent temozolomide at 75mgs / m² along with DSF – Cu followed by adjuvant temozolomide at 150mgs / m² for 6 -12 cycles in patients with previously untreated, (aside from surgical resection), unmethylated glioblastoma.

Preclinical studies have identified DSF-Cu as having promising activity in glioblastoma cells and can potentially sensitize temozolomide-resistant cells to temozolomide.

A recent phase I study has demonstrated the feasibility and safety of combining DSF with adjuvant temozolomide in newly diagnosed glioblastoma patients after chemoradiotherapy (Huang, et al. 2016). This clinical trial will evaluate whether the addition of DSF-Cu to temozolomide in patients expected to be temozolomide-resistant can induce anti-tumor responses and validate the potential of DSF-Cu to sensitize glioblastoma to temozolomide.

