3.1 Inclusion Criteria

1. Age 18 or older
2. Diagnosis of histologically confirmed glioblastoma (WHO grade IV). Subjects with an original histologic diagnosis of low grade glioma or anaplastic glioma (WHO

- grade II or III) are eligible if a subsequent histological diagnosis of glioblastoma is made
3. Patients whose tumor is determined to be unmethylated
 4. Patients with incomplete resection as determined by residual, measurable gadolinium or contrast-enhancing lesion or lesions
 5. Recent resection of glioblastoma. Patients who have only had a tumor biopsy and who are considered unresectable are eligible (but based on the study accrual this subset of patients with unresectable tumor may be considered for separate analysis)
 6. ECOG PS of ≤ 2 (see appendix A)
 7. Willing to remain abstinent from consuming alcohol while on DSF
 8. No prior radiation or chemotherapy
 9. Meets the following laboratory criteria:
 - a. Absolute neutrophil count $\geq 1,500/\text{mcL}$
 - b. Platelets $\geq 100,000/\text{mcL}$
 - c. Hemoglobin $> 10.0 \text{ g/dL}$ (transfusion and/or ESA allowed)
 - d. Total bilirubin and alkaline phosphatase $\leq 2x$ institutional upper limit of normal (ULN)
 - e. Aspartate aminotransferase (AST) and alanine aminotransferase (ALT) $< 3 \times$ ULN
 - f. Blood urea nitrogen (BUN) and creatinine $< 1.5 \times$ ULN
 10. Able to take oral medication
 11. Able to understand and willing to sign an institutional review board (IRB)-approved written informed consent document (legally authorized representative permitted)
 12. MRI with and without contrast prior to enrollment.

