4.0 TREATMENT PLAN

This study is a single arm, open-label, phase II study of DSF-Cu in combination with concurrent temozolomide and radiation therapy followed by DSF – Cu and adjuvant temozolomide for patients with unmethylated tumors.

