9.0 STUDY CALENDAR

Screening/baseline evaluations are to be conducted within 4 weeks (+/- 7 days) prior to start of protocol therapy. Scans will be performed prior to the start of the protocol therapy. Each treatment cycle is 28 days.

	Screening / Baseline	Weekly during radiation treatment	Start of Fourth Week of radiation therapy	Day 1 of Each Cycle (+/- 7 days)	End of Every Even-Numbered Cycle	Day 1 of Cycle 1 (+/- 7 days)	Day 1 of Cycle 4 (+/- 7 days)	End of Treatment	Follow-Up ¹
Informed consent	X								
H&P incl. neurologic exam, ECOG	X			X				X	
Evaluation of corticosteroid usage	X		X	X					
CBC	X	X		X					
CMP	X			X					
Copper, blood	X					X	X		
Pregnancy testing (if applicable)	X								
Edmonton Symptom Assessment System – Revised (ESAS-r) QOL Questionnaire	X		X	X				X	
Brain MRI prior to enrollment	X				X ²			X	
Temozolomide				Concurrent radiation with temozolomide on days 1-42 at 75 mg/m ² . ³ Responding patients will subsequently receive adjuvant TMZ 150 mg/m ² Days 1-5 of each following 28 day cycle ³					
Disulfiram				Days 1-28 of each cycle ⁴					
Copper gluconate				Days 1-28 of each cycle ⁴					
AE assessment			X	X	X	X	X	X	X

1. Follow-up will be as clinically indicated. A chart review will be done at 2 years after the last dose of DSF to look for progression and survival.
2. A confirmatory MRI should be considered in 8 weeks after documentation of complete response (CR) or partial response (PR) if consistent with the institutional standard of care
3. To be taken at bedtime on an empty stomach. Must not be taken within an hour of DSF.
4. To be taken two times a day with meals.
5. AEs will be tracked for 30 days after the last dose of DSF.

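### The study calendar schedules no chemistry panel between screening and adjuvant Cycle 1 Day 1, nominally 8 to 9.5 weeks into treatment, so silent liver-test rises during chemoradiation would not be measured

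*Combined protocol and SAP*

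**What the plan says.** Section 6.3.1 sets the hepatic rule: "DSF-Cu should only be administered if hepatic function is within the parameters established in the eligibility criteria". It goes on to say that "hepatic dysfunction that occurs while the patient is on study should prompt an evaluation to determine the cause". The numeric limits are in Section 3.1: total bilirubin and alkaline phosphatase at or below 2 times the upper limit of normal (ULN), and AST and ALT below 3 times ULN. Section 6.3 separately allows one 50% dose reduction for DSF-related non-hematologic toxicity of grade 2 or higher.

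Section 4.0 describes the treatment as "DSF-Cu in combination with concurrent temozolomide and radiation therapy", followed by DSF-Cu with adjuvant temozolomide. DSF-Cu is therefore given during chemoradiation.

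The Section 9.0 calendar has two radiation-phase columns, "Weekly during radiation treatment" and "Start of Fourth Week of radiation therapy". The weekly column carries the CBC. The fourth-week column carries corticosteroid use, the ESAS-r questionnaire and an adverse-event assessment. The CMP row is blank in both; it is marked only at screening and on Day 1 of each cycle (+/- 7 days). Section 4.3 adds visits about every 4 weeks, but names only ECOG status and corticosteroid use as recorded at each one.

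**The concern.** A limit defined by laboratory values can be applied on treatment only if the laboratory test is done. During chemoradiation, when DSF-Cu, radiation and temozolomide are first given together, no liver test is scheduled. Symptomatic toxicity has a planned check at the start of radiation week 4. An asymptomatic rise in enzymes or bilirubin has none.

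Three parts of the plan depend on such a rise being seen: the on-study evaluation in Section 6.3.1, the grade 2 dose-reduction rule in Section 6.3, and the toxicity endpoint in Section 10.2, which tabulates DSF-related events by type and grade. Section 2.2 makes the safety of DSF-Cu given concurrently with temozolomide a secondary objective.

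A liver signal is on record. Section 1.9 reports that in men with prostate cancer "treated with 250-500 mg of DSF alone, grade 3 toxicities included double vision, hearing loss, LFT abnormality, diarrhea, constipation, and ataxia". This trial gives 250 mg per day, the low end of that range. The phase I glioblastoma study described in Sections 1.7 and 1.10 gave DSF after chemoradiotherapy and without copper, so it does not cover the combination used here during radiation.

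**Working it through.** The plan states no figure for this gap, so there is nothing to reproduce. The check is a reading of the calendar followed by schedule arithmetic.

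**Which cycle is Cycle 1?** Section 4.3 ties copper levels to Cycles 1 and 4 of adjuvant temozolomide. Section 4.4 lets Optune start by Day 1 of Cycle 1 but only once radiation is complete. The temozolomide row of the calendar places the 28-day cycles after the 42-day concurrent phase. All three make Cycle 1 the first adjuvant cycle.

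**Inputs.**
- Radiation: Section 1.11 gives 6 to 6.5 "weeks of radiation with concurrent temozolomide". Section 4.2 gives 23 + 7 = 30 fractions; at an assumed 5 per week that is 6 weeks, or 42 days, matching the concurrent temozolomide phase.
- Rest before adjuvant treatment: 2 to 3 weeks (Section 4.2).
- Visit window at Day 1 of each cycle: +/- 1 week (Section 9.0).
- Screening: up to 4 weeks, +/- 1 week, before the start (Section 9.0).
- Assumption: DSF-Cu starts on radiation day 1. Sections 1.11 and 4.0 support this, but no start day is stated.
- Assumption: the CMP carries the liver tests. It is the only chemistry panel in the plan.

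**Time from treatment start to first scheduled on-treatment CMP** = radiation + rest.
- Shortest: 6 + 2 = 8 weeks; with the window, 8 - 1 = 7.
- Longest: 6.5 + 3 = 9.5 weeks; with the window, 9.5 + 1 = 10.5.
- Using Section 4.2 alone (42 days plus rest): 6 + 2 = 8 to 6 + 3 = 9 weeks.
- If DSF-Cu starts 1 week after radiation begins: 7 to 8.5 weeks on DSF-Cu. If 2 weeks after: 6 to 7.5 weeks.

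**Gap between consecutive scheduled CMPs**, with screening 4 weeks before the start: 8 + 4 = 12 to 9.5 + 4 = 13.5 weeks. With both windows at their limits it is at most 9.5 + 1 + 5 = 15.5 weeks.

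**Scheduled during 6 to 6.5 weeks of radiation:** about 6 to 7 CBCs, 1 adverse-event assessment, 0 CMPs.

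**Longest on-treatment gap after a change to the calendar** (the start of week 4 is 3 weeks in):

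| Panels added | Intervals (weeks) | Longest, nominal | Longest, with window |
|---|---|---|---|
| None | 8 to 9.5 | 8 to 9.5 | 10.5 |
| Start of week 4 | 3; then 8 - 3 = 5 to 9.5 - 3 = 6.5 | 5 to 6.5 | 7.5 |
| Start of week 4 and end of radiation | 3; 6 - 3 = 3 to 6.5 - 3 = 3.5; rest 2 to 3 | 3 to 3.5 | 3 + 1 = 4 |

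The last row assumes the second panel is drawn as radiation ends. If the last weekly draw comes up to 1 week earlier, the final interval lengthens by up to 1 week, to at most 3 + 1 = 4 weeks nominal and 5 with the window.

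**The case against.** The blank calendar cells are not in dispute. The case on the other side has four parts.

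**The liver risk looks low.** Section 6.3.1 calls hepatic toxicity uncommon. Table 2 (Section 4.3) lists hepatitis as rare, meaning 1% or less. Table 1 (Section 1.9) shows no hepatic grade 2-3 event among 7 + 5 = 12 patients on 500 to 1000 mg of DSF with adjuvant temozolomide. Section 1.10 describes 250 mg of DSF with 6 mg of copper as well tolerated in patients with liver metastases. Section 1.9 reports no liver damage in rats on long-term high doses, and its grade 3 LFT finding in men comes without a count or the dose at which it occurred. Section 3.2 excludes severe hepatic disease. This lowers the weight of the point but does not remove it. Hepatitis is not the same as an asymptomatic enzyme rise, for which the documents give no rate. Table 1 concerns few patients, without copper or concurrent radiation.

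**Section 6.3.1 may be a starting threshold only.** On that reading the screening CMP satisfies its first sentence and nothing is contradicted. This is fair, and no flat contradiction is claimed. The request to evaluate dysfunction that arises on study remains, and a silent rise cannot prompt it without a test.

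**The word cycle is ambiguous.** The calendar's only DSF entry is days 1 to 28 of each cycle, although DSF is also given during radiation. The 4-weekly visits require ECOG status, which the calendar marks on treatment only in the Day 1 column (and again at end of treatment); that Day 1 column also carries CMP. If chemoradiation counted as cycles, a CMP would fall near day 29. Sections 4.3 and 4.4, the temozolomide row and the separate radiation columns go against this reading, but the calendar could be clearer.

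**The upper end of the range is generous.** The 9.5 weeks pairs the rationale's 6.5 weeks with the rest period in Section 4.2; Section 4.2 alone gives 8 to 9 weeks. That is correct and changes little.

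**Conclusion.** The concern holds in a narrow form. The calendar schedules no liver test during chemoradiation, and the first on-treatment one falls nominally at 8 to 9.5 weeks (7 to 10.5 with the window). This rests on three things: DSF-Cu starting with radiation, the CMP carrying the liver tests, and Cycle 1 being adjuvant. The last is well supported by the text. A DSF-Cu start 1 to 2 weeks later still leaves 6 to 8.5 weeks.

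The consequence is limited to safety monitoring and toxicity capture. A rise that comes and goes before Cycle 1 Day 1 may never be recorded; one that persists is found late. Unscheduled testing under routine care could reduce this, but the plan does not require it. How many rises would be missed cannot be computed from the documents. ORR, PFS6, OS, the sample size and the error rates are untouched. The correction is worth making because it is so cheap.

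**What to change.** In Section 9.0, mark a CMP or liver panel at the start of the fourth week of radiation, taken with that week's CBC and read alongside the adverse-event assessment already planned then. Preferably mark a second panel at the last weekly draw of radiation. A footnote stating that cycles are counted from the start of adjuvant treatment, and giving the DSF-Cu start day, would remove the ambiguity in the calendar.

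The cost is one or two laboratory tests per patient on blood already being drawn: 14 x 1 = 14 to 14 x 2 = 28 tests for 14 patients, or 40 x 1 = 40 to 40 x 2 = 80 for 40. No visit or venepuncture is added. The downside is a small laboratory cost and possibly a few more dose holds.
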